6.6.4 Other Allowed Dose Interruptions

If the participant is receiving treatment with lenvatinib and requires surgery during the study, the stop time and restart time of lenvatinib should be as follows:

- For minor procedures: stop lenvatinib at least 2 days before the procedure and restart it at least 2 days after, once there is evidence of adequate healing and no risk of bleeding.
- For major procedures: stop lenvatinib at least 1 week (5 half-lives) prior to surgery and then restart it at least 2 weeks after, once there is evidence of adequate healing and no risk of bleeding.
- For scheduled dental surgery or invasive dental procedures, stop lenvatinib for at least 1 week before the procedure, then restart lenvatinib when deemed clinically appropriate.

The reason for interruption should be documented in the participant's study record.

6.7 Intervention After the End of the Study

The study is complete upon consent of the last active treatment participant in an extension study using pembrolizumab monotherapy, coformulations, or in combination with a compound (eg, Lenvatinib), if available.

All study related procedures and data collection as defined per protocol will be terminated at study completion. In addition, survival follow-up will be stopped upon study completion as defined in Section 4.4.

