4.4 Beginning and End of Study Definition

The overall study begins when the first participant (or their legally acceptable representative) provides documented informed consent. The overall study ends when the last participant completes the last study-related telephone-call or visit, withdraws consent, is lost to follow-up (ie, the participant is unable to be contacted by the investigator), or the last participant on active treatment is consented in an extension study.

For purposes of analysis and reporting, the overall study ends when the Sponsor receives the last laboratory test result or at the time of final contact with the last participant, whichever comes last.

If the study includes countries in the European Economic Area (EEA), the local start of the study in the EEA is defined as First Site Ready in any Member State.

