6.6.1 Pembrolizumab

6.6.1.1 Immune-Related Events and Dose Modification (Withhold, Treat, Discontinue)

Dose Modification and Toxicity Management for Immune-related AEs Associated with Pembrolizumab

AEs associated with pembrolizumab exposure may represent an immune-related response. These irAEs may occur shortly after the first dose or several months after the last dose of pembrolizumab treatment and may affect more than one body system simultaneously. Therefore, early recognition and initiation of treatment is critical to reduce complications. Based on existing clinical study data, most irAEs were reversible and could be managed with interruptions of pembrolizumab, administration of corticosteroids and/or other supportive care. For suspected irAEs, ensure adequate evaluation to confirm etiology or exclude other causes. Additional procedures or tests such as bronchoscopy, endoscopy, skin biopsy may be included as part of the evaluation. Based on the severity of irAEs, withhold or permanently discontinue pembrolizumab and administer corticosteroids.

Dose Modification and Toxicity Management Guidelines for irAEs associated with pembrolizumab monotherapy, coformulations, or IO combinations are provided in [Table 3](#).

See Section 10.7 (Appendix 7) for country-specific requirements.

Table 3 Dose Modification and Toxicity Management Guidelines for Immune-related Adverse Events Associated with Pembrolizumab Monotherapy, Coformulations or IO Combinations

General instructions:				
irAEs	Toxicity Grade (CTCAEv4.0)	Action With Pembrolizumab Monotherapy, Coformulations or IO Combinations	Corticosteroid and/or Other Therapies	Monitoring and Follow-up
Pneumonitis	Grade 2	Withhold	
 Administer corticosteroids (initial dose of 1-2 mg/kg prednisone or equivalent) followed by taper 	
 Monitor participants for signs and symptoms of pneumonitis Evaluate participants with suspected pneumonitis with radiographic imaging and initiate corticosteroid treatment Add prophylactic antibiotics for opportunistic infections
	Recurrent Grade 2 or Grade 3 or 4	Permanently discontinue		

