8.4 Adverse Events (AEs), Serious Adverse Events (SAEs), and Other Reportable Safety Events

The definitions of an AE or SAE, as well as the method of recording, evaluating, and assessing causality of AE and SAE and the procedures for completing and transmitting AE, SAE, and other reportable safety event reports can be found in Appendix 3.

Progression of the cancer under study is not considered an AE as described in Section 8.4.6 and Appendix 3.

Adverse events, SAEs, and other reportable safety events will be reported by the participant (or, when appropriate, by a caregiver, surrogate, or the participant's legally authorized representative).

The investigator and any designees are responsible for detecting, documenting, and reporting events that meet the definition of an AE or SAE as well as other reportable safety events. Investigators need to document if an SAE was associated with a medication error, misuse, or abuse.

Investigators remain responsible for following up AEs, SAEs, and other reportable safety events for outcome according to Section 8.4.3. The investigator, who is a qualified physician, will assess events that meet the definition of an AE or SAE as well as other reportable safety events with respect to seriousness, intensity/toxicity and causality.

8.4.1 Time Period and Frequency for Collecting AE, SAE, and Other Reportable Safety Event Information

All AEs, SAEs, and other reportable safety events that occur after the participant provides documented informed consent but before intervention allocation/randomization must be reported by the investigator if the participant is receiving placebo run-in or other run-in treatment, if the event cause the participant to be excluded from the study, or is the result of a protocol-specified intervention, including but not limited to washout or discontinuation of usual therapy, diet, or a procedure.

- All AEs from the time of intervention allocation/randomization through 30 days following cessation of study intervention must be reported by the investigator.
- All AEs meeting serious criteria, from the time of intervention allocation/randomization through 90 days following cessation of study intervention or 30 days following cessation of study intervention if the participant initiates new anticancer therapy, whichever is earlier, must be reported by the investigator.

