10.7.2 Germany

Section 1.3 Schedule of Activities

SAEs will be monitored for 120 days after the last dose of study intervention.

Pregnancy testing will be continued for 120 days after the last dose of study intervention, regardless of initiation of subsequent anticancer therapy.

Section 5.2 Exclusion Criteria

- Has a known history of HIV infection. HIV testing is required at Screening.
- Has a known history of Hepatitis B (defined as Hepatitis B surface antigen [HBsAg] reactive) or known active Hepatitis C virus (defined as HCV RNA [qualitative] is detected) infection. Testing for Hepatitis B or Hepatitis C is required at Screening.
- Has a known history of active tuberculosis (TB; *Bacillus tuberculosis*). Testing for tuberculosis is required at Screening.

Section 10.2 Appendix 2: Clinical Laboratory Tests

- Other screening tests: tuberculosis

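### If an extension study is available, Section 6.7 ends all data collection when the last treated participant consents to it, with no exception for recent discontinuers still inside the Section 8.4.1 safety windows

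*Combined protocol and SAP*

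**What the plan says.** Section 6.7 sets the trigger: "The study is complete upon consent of the last active treatment participant in an extension study", provided that an extension is available. The consequence is general: "All study related procedures and data collection as defined per protocol will be terminated at study completion". A separate sentence then stops survival follow-up at completion as defined in Section 4.4.

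Section 4.4 lists the same event as one of several ways in which the study can end: "or the last participant on active treatment is consented in an extension study". For analysis and reporting it gives another end: "the overall study ends when the Sponsor receives the last laboratory test result or at the time of final contact with the last participant", whichever is later. The synopsis words the extension event differently again, as planned enrolment and not consent.

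The safety rules run on each participant's own clock:

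- Section 8.4.1, AEs: all, to 30 days after study intervention stops.
- Section 8.4.1, SAEs (the earlier of two dates applies): all, "through 90 days following cessation of study intervention or 30 days following cessation of study intervention if the participant initiates new anticancer therapy".
- Section 8.4.1, pregnancy and breastfeeding exposure: 120 days after pembrolizumab or 30 days after lenvatinib, whichever is last; 30 days if new anticancer therapy starts.
- Appendix 7, Germany: "SAEs will be monitored for 120 days after the last dose of study intervention".
- Section 8.10.4.1: a mandatory Safety Follow-up Visit about 30 days after the last dose.
- Section 7.1: collection continues through the last scheduled follow-up, even after treatment has been discontinued.

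The extension paragraph in Section 8.4.1 hands safety reporting over to the extension study, but only for those who enter it.

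**The concern.** The two sets of rules use different clocks. The safety windows run from each participant's own last dose. The cut-off in Section 6.7 is fixed by another participant's consent and takes no account of who is still in post-treatment follow-up. For a participant who stopped shortly before the trigger and stays out of the extension, a site cannot follow both Section 6.7 and Section 8.4.1.

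Safety is a primary objective, and Section 9.4.2 names treatment-emergent AEs, SAEs and discontinuation due to AEs as primary safety endpoints. The exposed group includes people who stopped for toxicity. Section 6.6.1.1 says that immune-related events "may occur shortly after the first dose or several months after the last dose of pembrolizumab treatment", so the truncated period is one in which events are expected.

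**Working it through.** The plan states no figure for this point, so the check compares the texts and then counts days.

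**1. Does the termination sentence reach safety data?** Yes, as written. It covers all procedures and data collection. It cannot be read as meaning survival follow-up only, because the next sentence stops survival follow-up separately.

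**2. Does another section restore the windows?**

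| Section | What it preserves | Does it close the gap? |
|---|---|---|
| 8.4.1, extension paragraph | Reporting for those who enter the extension | No: silent on those who do not |
| 4.4, end for analysis and reporting | A later date for analysis | No: it does not reopen collection that Section 6.7 has stopped |
| 8.4.1, outside the windows | SAEs considered related that come to the investigator's attention | In part: there is no duty to look for events in former participants |
| 8.4.3 | Follow-up of reported events to resolution or stabilization | In part: it does not collect new events |
| 10.3.6 | Paper or telephone route for SAEs once electronic data collection is off-line | In part: a route only |

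None of these keeps active, all-causality collection or the 30-day visit.

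**3. Days lost.** Let d be the days between stopping treatment and the trigger, and W the window. For a participant who does not enter the extension:

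days lost = max(0, W − d)

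W is 30 (AEs), 90 (SAEs with no new anticancer therapy), and at most 120 (pregnancy, if pembrolizumab was stopped on the same day; SAEs in Germany).

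| d | AEs (W = 30) | SAEs (W = 90) | Pregnancy, or SAEs in Germany (W = 120) |
|---|---|---|---|
| 0 | 30 | 90 | 120 |
| 10 | 20 | 80 | 110 |
| 20 | 10 | 70 | 100 |
| 30 | 0 | 60 | 90 |
| 60 | 0 | 30 | 60 |
| 90 | 0 | 0 | 30 |

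Worked case, d = 20: AEs 30 − 20 = 10 days; SAEs 90 − 20 = 70 days. If new anticancer therapy has started, W for SAEs and pregnancy under Section 8.4.1 is 30, so each loses 30 − 20 = 10 days. The German text does not say whether the SAE window also shortens in that case.

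**4. Who is exposed?** Those whose last dose falls within 90 days before the trigger (120 for pregnancy and for SAEs in Germany) and who do not enter the extension. For d below 30, the mandatory visit would ordinarily still be ahead as well. The documents do not allow a count.

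**5. What could change in the results?** A participant who stopped for an AE already counts in the AE and discontinuation summaries. A count moves only if the truncated days contain the participant's first AE or SAE, a new preferred term or a higher grade. One missed first SAE shifts an SAE proportion by 1/100 = 1.0 percentage point in a cohort of 100, and by 1/30 = 3.3 points in a group of 30.

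**The case against.** The strongest reply is that the protocol is less absolute than Section 6.7 looks in isolation. Much of that reply stands:

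- **Completion does not hang on one event.** A reader might infer that it does. Section 4.4 lists several end events and a separate end for analysis and reporting, and the Section 6.7 trigger applies only if an extension is available.
- **The loss is not total.** A reader might infer that all safety information on these participants disappears. The documents do not support that. Related SAEs that reach the investigator remain reportable at any time, and a reporting route exists after electronic collection closes. A late immune-related SAE recognised as such is among the events most likely to be caught.
- **The 70-day figure is conditional.** It falls to 10 once new anticancer therapy starts. The 120-day pregnancy window also does not apply to everyone: for a participant on lenvatinib alone whose pembrolizumab ended more than 90 days before lenvatinib stopped, the window is 30 days after lenvatinib.
- **Not every primary safety endpoint is exposed.** Discontinuation due to AEs cannot change after discontinuation, and no hypothesis test is planned.
- **The extension's entry rules are not in these documents.** That recent discontinuers would stay outside it is plausible but not shown.

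These points limit the scale. They do not remove the conflict: no section exempts post-treatment safety follow-up from the termination sentence. The analysis-and-reporting definition does not do so either, because ending procedures early may itself bring forward the final contact.

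**Conclusion.** The point holds as a conflict between stated rules. If an extension is available, following Section 6.7 literally cuts short safety collection that Sections 7.1, 8.4.1, 8.10.4.1 and Appendix 7 require for recent discontinuers who do not enter it.

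The loss per person is at most 30 days of AE collection and 90 days of SAE collection (120 in Germany). It is limited to active, all-causality ascertainment: new nonserious AEs, SAEs not considered related, and related SAEs that nobody brings to the investigator. The number affected is not stated and is probably small, since only the last few months before the trigger matter in a study estimated at about 70 months. That the SAE proportion is materially understated is a possible inference, but the documents give no basis for quantifying it.

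The conclusion assumes that an extension opens, that at least one participant stops within a window before the last consent, and that this participant does not enter the extension. It is worth correcting because it touches a primary objective and costs little.

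**What to change.** Reconcile Sections 6.7 and 4.4 and the synopsis with Section 8.4.1. Add an exception to the termination sentence in Section 6.7: participants who do not enter the extension complete the safety follow-up already set by Sections 8.4.1 and 8.10.4.1 and Appendix 7 before their safety data collection ends, while survival and efficacy follow-up may stop at the trigger. Cross-refer to this in Section 4.4 and the synopsis, and use the same extension event (consent or planned enrolment) in all three places.

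An exception is better than moving the completion date. Section 6.7 ties survival follow-up to completion, so a later date would prolong that as well.

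The cost is a few sentences in three places. Safety data collection may stay open for up to about 90 to 120 days for a few participants. No new procedures are needed.

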6.8 Clinical Supplies Disclosure

This study is open-label; therefore, the participant, the study site personnel, the Sponsor, and/or designee are not blinded. Study intervention (name, strength, or potency) is included in the label text; random code/disclosure envelopes or lists are not provided.

7 DISCONTINUATION OF STUDY INTERVENTION AND PARTICIPANT WITHDRAWAL

7.1 Discontinuation of Study Intervention

Discontinuation of study intervention does not represent withdrawal from the study.

As certain data on clinical events beyond study intervention discontinuation may be important to the study, they must be collected through the participant's last scheduled follow-up, even if the participant has discontinued study intervention. Therefore, all participants

who discontinue study intervention prior to completion of the protocol-specified treatment period regimen will still continue to participate in the study as specified in Section 1.3 (SoA) and Section 8.10.4.

Participants may discontinue study intervention at any time for any reason or be discontinued from the study intervention at the discretion of the investigator should any untoward effect occur. In addition, a participant may be discontinued from study intervention by the investigator or the Sponsor if study intervention is inappropriate, the study plan is violated, or for administrative and/or other safety reasons. Specific details regarding procedures to be performed at study intervention discontinuation are provided in Section 8.1.10.

A participant must be discontinued from study intervention but continue to be monitored in the study for any of the following reasons:

- The participant or participant's legally acceptable representative requests to discontinue study intervention.
- Any prolonged interruption of study intervention beyond the permitted periods, for irAE management or other allowed dose interruptions, as noted in Sections 6.6.1, 6.6.2, and 6.6.4 require sponsor consultation prior to restarting treatment. If treatment will not be restarted, the participant will continue to be monitored in the study and the reason for discontinuation of study intervention will be recorded in the medical record.
- The participant has a medical condition or personal circumstance which, in the opinion of the investigator and/or Sponsor, placed the participant at unnecessary risk from continued administration of study intervention.
- The participant has a positive serum or urine pregnancy test at any time during the course of the study.
- Initiation of a new anticancer treatment.
- Administrative reasons requiring cessation of treatment.
- Any progression or recurrence of any malignancy, or occurrence of another malignancy that requires active treatment. Exceptions to secondary malignancy include basal cell carcinoma of the skin, squamous cell carcinoma of the skin, new nonulcerated primary melanoma <1 mm in depth with no nodal involvement, or carcinoma in situ (eg, breast carcinoma, cervical cancer in situ) that have undergone potentially curative therapy. Exceptions should be discussed with the Sponsor before continuing therapy or remaining in follow-up.
- Confirmed radiographic disease progression outlined in Section 8.2.1.5 or Section 8.2.1.6.

Note: Participants will be permitted to continue treatment beyond iRECIST- or RANO-defined progression (Arm 1 only) after confirming informed consent addendum has been documented and after Sponsor consultation.

- Unacceptable AE(s).

A participant may be discontinued from study intervention but continue to be monitored in the study for the following reason:

- PD as determined by the investigator.

Note: Participants will be permitted to continue treatment beyond RECIST 1.1- or RANO-defined progression (Arm 1 only) as long as investigator-assessed clinical stability is observed, the participant is tolerating study intervention (Section 8.2.1.5 or Section 8.2.1.6) and after obtaining documented informed consent addendum. Treatment beyond confirmed PD per iRECIST or RANO may be permitted on Sponsor consultation.

Participants receiving the combination therapy (pembrolizumab + lenvatinib) must discontinue study therapy if any of the following occur:

ALT or AST elevation meeting the following criteria:

- ALT or AST $>5 \times$ ULN for more than 2 weeks

Pembrolizumab will have already been permanently discontinued per [Table 3](#) but lenvatinib may be administered at a reduced dose by the time this criterion is met and must be permanently discontinued immediately.

- ALT or AST $>3 \times$ ULN and (TBL $>2 \times$ ULN or INR >1.5)

Although [Table 3](#) advises pembrolizumab to be withheld (interrupted), and [Table 5](#) advises lenvatinib to have no dose modification or a reduction, if this criterion is met, both interventions must be permanently discontinued immediately.

Completion of pembrolizumab q3w consists of 35 treatments (approximately 2 years). Note: participants experiencing a clinical benefit, according to the PI, may continue on lenvatinib beyond this time point with Sponsor consultation. Discontinuation of treatment may be considered for participants who have attained a confirmed CR and have been treated for at least 8 cycles (at least 24 weeks), receiving 2 cycles of the combination including 2 doses of pembrolizumab and at least 80% of the planned doses of lenvatinib beyond the date when the initial CR was declared.

7.2 Participant Withdrawal From the Study

It has been well-documented that a higher rate of withdrawal can render a study uninterpretable; therefore, unnecessary withdrawal of participants should be avoided.

As clinical event data are important study endpoints, participants who discontinue study intervention prior to completion of the treatment period should be encouraged to continue all remaining study visits for follow-up and vital status assessment as outlined in the SoA and Section 8.10.4.

The investigator is to inform the participants that:

- they may discontinue from study intervention at any time during the study, and
- they are encouraged to continue visits in the study for follow-up, imaging, and vital status assessment.

If participants elect to stop study procedures, they are encouraged to continue to be followed, which allows periodic survival follow-up and vital status data to be collected.

If a participant fails to return for scheduled visits and/or if the study site is unable to contact the participant after multiple attempts (ie, is lost to follow-up), the procedures to be performed are outlined in Section 7.3.

If a participant decides not to continue receiving study intervention, the participant is to be encouraged to continue visits in the study for follow-up, imaging, and vital status assessment.

Participants who withdraw consent during the study

If the participant or participant's legally acceptable representative withdraws consent, the participant must be withdrawn from the study.

Section 8.1.10 delineates the specific procedures performed at the time of withdrawal.

Any AEs that are present at the time of withdrawal should be followed in accordance with the safety requirements outlined in Section 8.4.

